## **2.0 INTRODUCTION**

[figure not shown]
#### 2.1 Abstract

The proposed clinical trial is a dose escalation study of rAAVrh74.MCK.GALGT2 for DMD patients. There will be a modified intravascular limb infusion(ILI);

 henceforth designated as intravascular limb infusion for gene therapy (ILI-GT) delivered sequentially to the whole each lower limb of DMD subjects via a major lower limb artery.

ILI-GT will be delivered to the muscles of both legs of DMD subjects. This approach to vascular gene transfer builds upon previously published methods used in mice and non-human primates.

Two cohorts will undergo gene transfer in a standard dose escalation scheme to establish maximum tolerated dose (MTD) using toxicity. One subject will be enrolled into the first cohort and one subject will be enrolled in the second cohort. The first cohort will receive the minimally efficacious dose as established by primate studies, consisting of  $2.5 \times 10^{13}$  vg/kg per leg, delivered bilaterally (to total  $5.0 \times 10^{13}$  vg/kg per subject). Once safety is established in the low-dose cohort, the second cohort will receive  $5 \times 10^{13}$  vg/kg per leg, delivered bilaterally (to total  $1.0 \times 10^{14}$  vg/kg per subject).

The baseline open muscle biopsy will be performed in one quadriceps muscle. Open muscle biopsy of the quadriceps (in the leg contralateral to the pre-treatment biopsy) will be performed at 90 days post ILI-GT procedure.

Every effort

will be made to sample these same muscles in all patients; however, in subjects (particularly older ambulant subjects) with limited quadriceps musculature, alternate muscle biopsy sites may be selected at the PIs discretion (including gastrocnemius or tibialis anterior muscles).

The primary objective of this study is the assessment of the safety of intravascular administration of rAAVrh74.MCK.GALGT2 to DMD patients. Safety endpoints will be assessed by changes in hematology, serum chemistry, urinalysis, immunologic response to

rAAVrh74 and GALGT2, and reported history and observations of symptoms. Efficacy measures will be used as secondary outcome for this disorder including a combination of functional 6 minute walk test (6MWT) and direct muscle testing for strength (MVICT) of lower limb muscles.

Subjects will be evaluated at baseline, infusion visit (days 0-2), and return for follow up visits on days 7, 14, 30, 60, 90, and 180 and months 12, 18 and 24.

#### 2.3 Background and Significance

#### 2.3.1 Disease Characteristics

DMD is the most common, severe childhood form of muscular dystrophy. Inheritance follows an X-linked recessive pattern. Birth prevalence has been estimated at 1 in 5000 live male births. Approximately one-third of cases represent new mutations of the *DMD* gene with the remaining inherited on the X chromosome from a carrier mother. Questions usually begin to surface between ages 3 to 5 regarding reduced motor skills that alert a need for diagnostic evaluation. DMD is relentlessly progressive with loss of ambulation occurring, in the precorticosteroid treatment era, by age 12. Historically patients died from respiratory complications, but improved pulmonary and ventilatory measures (including nocturnal ventilatory support) have further improved survival. Prolonged survival from in turn unmasks a decline in cardiac function, marked by dilated cardiomyopathy, raising additional treatment challenges in the late-stage patient.

#### 2.3.2 Disease Pathogenesis

Nearly 30 years ago, the *DMD* gene was cloned, defining the molecular basis of the disease and leading to the identification of dystrophin as the deficient protein in muscle from DMD patients. Dystrophin is a 427kDa cytoskeletal protein required for muscle fiber stability. Loss of this protein results in susceptibility to repeated cycles of necrosis and regeneration with satellite cell depletion, diminished regenerative capacity of the muscle, ending in fat and connective tissue replacement (fibrosis). The mutation spectrum within the DMD gene reveals that deletions of one or more exons are found in ~65% of cases clustered in two hotspot regions. Originally multiplex PCR kits were developed that were able to detect 95%-98% of all deletions, but improved molecular methods of diagnosis – including multiplex ligation-dependent probe amplification (MLPA), multiplex amplifiable probe hybridization (MAPH), and comparative genomic hybridization (CGH) allow screening of all exons for copy number variation, facilitating detection of deletions and duplications. Methods of direct sequence analysis of the entire coding region are now in routine use, allowing detection of nearly all clinically relevant disease mutations.

#### 2.3.3 Current Treatment for DMD

The only therapeutic approach that has clearly demonstrated unequivocal efficacy for treatment of DMD is treatment with the glucocorticoids prednisone or deflazacort. Treatment with one or another of these agents has been repeatedly shown to result in increased strength and delay loss of ambulation. Deflazacort has recently gained FDA approval for treatment of boys with DMD, based largely on a slightly more favorable side effect profile, and although it is not yet commercially available in the US many patients order it from overseas. However, treatment with these drugs is associated with significant side effects, including weight gain, Cushingoid features, hypertension, cataract formation, loss of bone density, vertebral compression fractures, long bone fractures, and behavioral problems. Molecular therapies provide a promising alternative to glucocorticoids. One approach is direct gene replacement. Other approaches include exon skipping and nonsense mutation suppression (or "readthrough"). Exon skipping utilizes antisense oligomers to induce altered pre-mRNA splicing to restore an open reading frame, and a single such agent (eteplirsen) has received FDA approval, based largely on a small but statistically significant increase in dystrophin expression. However, both exon skipping and the as-yet unapproved nonsense suppression approach would only be beneficial to small subsets of patients with appropriate mutations. For example, eteplirsen would be beneficial to only 13% of patients, and the nonsense suppression agent ataluren to only to 15%.

#### 2.3.4 Rationale for Gene Therapy using GALTGT2

Gene replacement with GALGT2 competes favorably with any of these alternative molecular strategies that are on the horizon. None of the molecular-based therapies are proven to work clinically to provide life-altering treatments. Surrogate gene therapy with GALGT2 has advantages over other molecular approaches because of the potential for one-time dosing; others would require life-long treatment ultimately be far more expensive and impractical than gene replacement therapy.

. This provides reasonable assurance for avoiding off target effects. This project builds upon expertise of our group in developing gene replacement therapy with micro-dystrophin by IM or vascular delivery. Overexpression of GALGT2 results in correction of pathology not only in mouse models of DMD, but also models of limb-girdle muscular dystrophy type 2D (due to mutations in alpha-sarcoglycan) and congenital muscular dystrophy type 1A (due to mutations in laminin alpha2). In boys with DMD, expectations from this form of treatment include protection against eccentric contraction related to membrane fragility from loss of dystrophin at the sarcolemma and increase force generation.

## 3.0 CLINICAL RESEARCH PLAN

#### 3.1 Study Population

subjects age 4 years and older, and with proven mutations of the *DMD* gene will be enrolled at Nationwide Children's Hospital for the gene transfer study. Subjects will encompass any ethnic or racial background.

#### 3.2 Inclusion/Exclusion Criteria

#### **Inclusion** Criteria

- 1. Ambulant patients age 4 years or older
- 2. Confirmed mutations in the *DMD* gene using a clinically accepted technique that completely defines the mutation
- 3. Measurably impaired muscle function, (defined as less than 80% of the predicted value for age 100 MWT), but with sufficient muscle preservation to ensure assessment of muscle transfection based on clinical evaluation by the PI and expert colleagues. This degree of preservation will include:
  - a. Ability to extend the knee fully against gravity
  - b. Preserved ambulation with ability to walk  $\geq$  350 meters during the 6MWT
  - c. A magnetic resonance image of the quadriceps showing preservation of sufficient muscle mass to permit transfection
- 4. Males of any ethnic or racial group will be eligible
- 5. Ability to cooperate with muscle testing
- 6. Stable dose of corticosteroid therapy (including prednisone, prednisolone, or deflazacort and their generic forms) for at least 12 weeks prior to gene transfer.

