The baseline evaluation will take place over two visits (one to two weeks apart). Because a preexisting antibody response would be exclusionary, ELISA and ELISpot testing will be performed at the first visit, allowing the results to be reviewed prior to the muscle biopsy with its attendant risks (including sedation). Prescribed and over the counter medications used in the prior two weeks will be recorded at the baseline visit and changes in these medications will be recorded during each subsequent visit. The PI will encourage participants to maintain the medication and supplements they are on at enrollment through the course of the study.

Subjects must already be on prednisone, prednisolone, or deflazacort for at least 12 weeks at time of enrollment as part of the inclusion criteria.

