#### 3.6.2 Pre Infusion Visit (Day -1)

Subjects will arrive to the Nationwide Children's Hospital within 24 hours prior to gene transfer. They will undergo a physical exam, a review of concomitant medications and updates to the medical history. Vital signs (heart rate, respiratory rate, temperature, and blood pressure) and weight will be obtained.

- The labs obtained on Day -1 will include:
- Complete blood cell count (CBC) and differential, platelets
- Aspartate aminotransferase (AST)/alanine transaminase (ALT)
- Gamma-glutamyl transpeptidase (GGT)\*
- Prothrombin time (PT)/activated partial thromboplastin time (PTT)
- Creatine kinase (CK)

\* For subjects taking drugs that potentially induce GGT synthesis through the cytochrome P450 system, the clinically significant range will be estimated at two times the levels obtained from the baseline screening test.

An ELISpot for T-cell responses to AAVrh74 and GALGT2 will also be performed.

In previous gene therapy studies at NCH, there has been observed an antigen specific T-cell response to the AAV vectors. This is an expected response between 2 - 4 weeks following gene transfer. One possible consequence to such antigen specific T-cell responses is clearance of the transduced cells and loss of transgene expression. All subjects will already be on prednisone, prednisolone, or deflazacort for 12 weeks at time of enrollment as part of the inclusion criteria. The standard clinical dose of prednisone or prednisolone is 0.75 mg/kg/day, and the standard clinical dose of deflazacort is 0.9 mg/kg/day. In order to dampen the host immune response to our AAV-based therapy, for each subject the glucocorticoid dose will be increased to prednisone or prednisolone 1.0 mg/kg/day, not to exceed 60 mg/day; subjects on deflazacort at enrollment will be placed on prednisone or prednisolone for the immediate peri-injection period. This prednisone dose will be delivered beginning one day prior to the gene transfer and only after passing all inclusion and exclusion criteria (in the event that a measure is repeated on Day -1). This corticosteroid regiment will be continued after gene transfer as discussed in Section 3.7.1, followed by a return to the pre-treatment corticosteroid regimen.

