			ges to the stud er multiple da	dy, parents will be r	e-conse	nted at th	neir next v	isit.										
					) and vis	its 8-10 v	vill be per	formed at	least 1 da	y precedi	ng the bio	psy.						
	
 
Muscle strength testing at baseline (days -45 to -1) and visits 8-10 will be performed at least 1 day preceding the biopsy.
 
An open muscle biopsy will be peformed on one leg at the baseline, and on the other leg at 3 months post gene transfer.
 
																	
	5 Pronbyl	actic prec	Inisolone/pre	dnisone taper begir	ns on Day	/-1 and is	stanered	according	to AST A	T and FI	ISnot resu	lts Antici	nate that	most subia	rts will be d	n nrednisol	one for up to	120 days
				st of the anesthesia					. to AST, AL	. 1, anu EL	Sportesu	its. Antici	pate tridt	most subje	.cs will be (	n preunisolo	me for up to	120 0035.
	7. Day 0 V	ital Signs	Heart rate, re	espiratory rate, puls	se oxime	try, temp	erature, a	nd blood j								nd at least e	very five min	utes during
				minutes post-infusi ontinue at post-trea												f/u visits wil	l be collecter	d at locally
				es include ALT, AST			33, 43, 73	, 3/10 5, 12	., 10, 0110 2		Post Sell	e aunarei	samples	scheduleu		., a visits Wil	. se concelet	actiocally

Note: There will be a flexibility of working days for each of the planned study visits including screening to adjust the schedule to any unanticipated event. The windows for each appointment are as follows:

- ٠
- ٠
- ٠
- Days 7 and  $14 \pm 2$  days Days 30  $\pm$  3 days Days 60 and 90  $\pm$  7 days Day 180, and Months 12, 18 and 24  $\pm$  14 days •

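### The 12-week steroid criterion is stated in two incompatible ways; separately, its infusion-anchored form guarantees only 39 to 76 days of stable dose at the functional baseline

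*Combined protocol and SAP*

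**What the plan says.** The Synopsis and Section 3.2 (inclusion criterion 6) require a stable dose of prednisone, prednisolone or deflazacort "for at least 12 weeks prior to gene transfer".

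Section 3.6.1 puts it differently: "Subjects must already be on prednisone, prednisolone, or deflazacort for at least 12 weeks at time of enrollment as part of the inclusion criteria". Section 3.6.2 repeats this: "All subjects will already be on prednisone, prednisolone, or deflazacort for 12 weeks at time of enrollment as part of the inclusion criteria". Both sections present themselves as restating the inclusion criterion. Both count to enrollment, a term the protocol does not define, and neither mentions a stable dose.

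Section 3.6.1 allows baseline measures from Day -45 to Day -1, split over two visits one to two weeks apart. The schedule of events (Table 2) marks the 6MWT, 100 m walk/run, NSAA and MVICT at Visit 1.

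On the effect of steroids, Section 2.3.3 says: "Treatment with one or another of these agents has been repeatedly shown to result in increased strength and delay loss of ambulation".

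The Synopsis analyses function as the within-subject difference before and after gene transfer. Section 3.5 describes an open-label design with two dose cohorts of one subject each, and there is no untreated control. Section 3.11 counts stabilization of the 6MWT, as well as a significant change, as a positive result.

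**The concern.** There are two separate problems.

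The first is textual. One eligibility criterion has two anchors (infusion and enrollment) and two contents (stable dose and being on drug). Two people screening the same subject could reach different answers, and both could cite the protocol.

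The second would remain even if Sections 3.6.1 and 3.6.2 were deleted. Criterion 6 fixes the run-in relative to the infusion, but the value against which every later functional result is compared is measured before the infusion, possibly more than six weeks before. The guaranteed stable period at that measurement is therefore shorter than 12 weeks.

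This matters because the protocol itself credits steroids with a gain in strength, and the functional comparison has no concurrent control to absorb such a gain. If a start or increase were still taking effect at Visit 1, later values could look better for reasons unrelated to the vector. Because stabilization counts as positive, a gain that merely offset decline could meet the criterion. A recent reduction could work the other way and hide a benefit. With one subject per dose, one such subject is the whole cohort.

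**Working it through.** The plan gives no figure of its own for the stable-dose interval at baseline, so there is none to reproduce. The check is date arithmetic followed by a comparison of readings.

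**Inputs**
- Run-in R = 12 x 7 = 84 days, counted back from Day 0 (Synopsis; Section 3.2, criterion 6).
- Baseline window: Day -45 to Day -1 (Section 3.6.1; the Table 2 footnote on strength testing gives the same window).
- Visit spacing: 7 to 14 days (Section 3.6.1). Functional tests are at Visit 1 and the anesthesia for the biopsy is at Visit 2 (Table 2).
- Latest Visit 1: if Visit 2 is no later than Day -1, Visit 1 is no later than about Day -1 - 7 = Day -8.

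**Step 1: stable days guaranteed at baseline under criterion 6**

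If Visit 1 falls d days before infusion, the guaranteed interval is 84 - d days and the shortfall against 12 weeks is d days.

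| Visit 1 | Guaranteed stable days | Weeks | Shortfall (days) |
|---|---|---|---|
| Day -45 | 84 - 45 = 39 | 5.6 | 45 |
| Day -31 | 84 - 31 = 53 | 7.6 | 31 |
| Day -15 | 84 - 15 = 69 | 9.9 | 15 |
| Day -8 | 84 - 8 = 76 | 10.9 | 8 |

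The range is 39 to 76 days, and it never reaches 84.

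**Step 2: who can be at the 39-day limit**
- *Criterion 6 alone governs.* Either a steroid start or a dose change can be as recent as 39 days at baseline.
- *All four places apply, with enrollment at or before Visit 1 (an assumption).* A start must be at least 84 days before Visit 1. For a Visit 1 on Day -45 that is at least 84 + 45 = 129 days before infusion. A dose change can still be 39 days old, because only criterion 6 speaks of stability.
- *All four places apply, with enrollment read as Day 0.* The anchors coincide, and 39 days is again the limit for both.

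A recent dose change is therefore possible on every reading of the text as written. A recent start is possible only if criterion 6 is in effect the sole rule.

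**Step 3: which follow-up comparisons are affected**

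For a subject 39 days past a change at baseline, the time since that change is 84 + 90 = 174 days at Day 90 and 84 + 180 = 264 days at Day 180. Section 3.6.2 also raises the steroid dose from Day -1, and Section 3.7.1.1 anticipates that course lasting up to 120 days. Since 90 < 120, it can cover the Day 90 tests. The Day 180 visit falls 180 - 120 = 60 days after its anticipated end.

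**Step 4: size of the bias**

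Section 2.3.3 gives a direction (more strength, later loss of ambulation) but neither a size nor a time course. Whether an effect is still developing 39 to 76 days after a change cannot be settled from the documents, so no bias is computed.

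**The case against.** The strongest reply is that the two statements can be satisfied together. A subject can be required to be on drug for 12 weeks at enrollment and also on a stable dose for 12 weeks at infusion. If enrollment is no later than Visit 1, recent starters are then excluded. This stands for starts, subject to the assumption about enrollment. It does not help with dose changes.

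Three stronger readings are tempting, and the documents do not support them:
- *The conflicting anchors produce the 39 days.* They do not. The figure follows from criterion 6 and the Day -45 window. The conflict only leaves open which rule governs.
- *Section 3.6.1 admits a subject whose dose changed just before enrollment.* It does not do so alone. It refers back to the inclusion criteria, and criterion 6 still applies.
- *The baseline is biased toward benefit.* The documents show only that it could be, and a recent reduction would push the other way.

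Two further objections limit what is at stake. Safety is the primary outcome and the functional measures are exploratory. With one subject per cohort no within-cohort paired test exists, and pooling both subjects leaves 1 degree of freedom (two-sided 5% critical t of 12.71). Functional change could not be firmly attributed to the vector whatever the run-in. In addition, the protocol's own steroid increase confounds Day 90, and no change to the run-in removes that. Both points stand. They lower the weight of the issue but do not excuse an avoidable second source of steroid variation in the later comparisons.

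**Conclusion.** The criterion is inconsistent between the Synopsis and Section 3.2 on one side and Sections 3.6.1 and 3.6.2 on the other, and the passages must be reconciled. Independently of that, criterion 6 guarantees only 39 to 76 days of stable steroid dose at the functional baseline, 8 to 45 days short of the 12 weeks it names.

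This rests on Visit 1 falling between about Day -45 and Day -8. The lower figure is the extreme edge of the window, not the expected case. The consequence is a possibility in either direction and of unknown size.

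The point is worth correcting because it is cheap and because the protocol defines a positive 6MWT result on an uncontrolled comparison. It does not touch the primary safety outcome. The benefit of correction lies mainly in the comparisons from month 6 onward, assuming the peri-infusion course has ended by then as anticipated and the subject has returned to the regimen in force at baseline. The Synopsis also reads the 6MWT at Day 90, and that reading stays confounded.

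**What to change.** 1. Reconcile the Synopsis, Section 3.2 (criterion 6), Section 3.6.1 and Section 3.6.2 to one criterion, with one anchor and one statement on whether the dose must be stable.
2. Define enrollment relative to consent, Visit 1 and infusion.
3. Have the sponsor state the required stability period relative to the baseline functional assessment, so that the baseline is not taken inside it. The length of the period is for the sponsor to set, and no change to any steroid dose is implied.
4. State in Section 3.11 or 3.12 that the Day 90 functional results may fall within the protocol's own steroid course and cannot be separated from it.

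Repeating the functional tests later is not a workable substitute. A subject with exactly 84 stable days at infusion reaches 12 weeks only on Day 0, under anesthesia and after the Day -1 steroid increase. A repeat after Visit 2 would follow the biopsy, whereas the Table 2 footnote puts baseline strength testing at least one day before it.

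The cost of items 1 to 3 is wording in four places. If the sponsor keeps 12 weeks and counts them to Visit 1, a recently adjusted subject would wait up to about 45 days longer. Item 4 adds one sentence.

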#### **Exclusion** Criteria

- 1. Active viral infection based on clinical observations.
- 2. The presence of a DMD mutation without weakness or loss of function
- 3. Subject is amenable to or is currently being treated with eteplirsen.
- 4. Symptoms or signs of cardiomyopathy, including:

- a. Dyspnea on exertion, pedal edema, shortness of breath upon lying flat, or rales at the base of the lungs
- b. Echocardiogram with ejection fraction below 40%
- 5. Serological evidence of HIV infection, or Hepatitis B or C infection
- 6. Diagnosis of (or ongoing treatment for) an autoimmune disease
- 7. Persistent leukopenia or leukocytosis (WBC  $\leq$  3.5 K/µL or  $\geq$  20.0 K/µL) or an absolute neutrophil count < 1.5K/µL
- 8. Concomitant illness or requirement for chronic drug treatment that in the opinion of the PI creates unnecessary risks for gene transfer
- 9. AAVrh74 binding antibody titers  $\geq$  1:50 as determined by ELISA immunoassay
- 10. Presence of circulating anti-Sda antibodies as determined by study approved laboratory.\*
- 11. Abnormal laboratory values in the clinically significant range in the Table 1 below, based upon normal values in the Nationwide Children's Hospital Laboratory:

System	Assay	Normal Range	Abnormal (Clinically Significant)			
Liver Function	GGT	8-80 U/L	> 80 U/L			
Liver Function	Total Bilirubin	0.1-1 mg/dL	$\geq$ 3 mg/dL			
Renal Function	Creatinine	0.3-1.mg/dL	>1.8 mg/dL			
	Platelet Count	140-440x10  platelets/mm 	$\leq$ 90 or $\geq$ 800 x 10  platelets/mm 			
Hematologic	Hemoglobin*	(g/dL) 2 - 6 yrs: 11.5-13.5 6 - 12 yrs: 11.5-15.5 12 - 18 yrs: Male: 13-15 Female: 12-16	For all ages: $\leq 8 \text{ or } \geq 18 \text{ g/dL}$			
	White Blood Cell Count	4 – 6 yrs: 5.5-15.5 6 – 10 yrs: 5-14.5 10 – 21 yrs: 4.5-13.5	For all ages: White blood cell count $\leq 3.5$ or $\geq$ 20 x 10  cells/mL Or Absolute neutrophil count of $\leq 1.5$ x 10  cells/mL			

Table 1 Normal and abnormal laboratory	values at Nationwide Children's Hospital Laboratory
	values at Nationwide Children's Hospital Laboratory

